#### 6.4. Study Intervention Compliance

When participants are dosed at the site, they will receive study intervention directly from the investigator or designee, under medical supervision. The date and time of each dose administered in the clinic will be recorded in the source documents. The dose of study intervention and study participant identification will be confirmed at the time of dosing by a member of the study site staff other than the person administering the study intervention. Study site staff will examine each participant's mouth to ensure that the study intervention was ingested.

When participants self-administer GSK3965193 or placebo CCI [REDACTED] during the site visits and documented in the source documents and relevant form. Deviation(s) from the prescribed dosage regimen should be recorded.

A record of the quantity of GSK3965193 or placebo CCI [REDACTED] dispensed to and administered by each participant must be maintained and reconciled with study intervention and compliance records. Intervention start and stop dates, including dates for intervention delays and/or dose reductions will also be recorded.

#### 6.5. Dose Modification

##### GSK3965193

Dose justification and stopping criteria are detailed in Section 4.5 and Section 7.1, respectively.

CCI [REDACTED]  
[REDACTED]  
[REDACTED]  
[REDACTED]  
[REDACTED]

##### Bepirovirsen

Dose modifications are not planned for this study.

#### 6.6. Continued Access to Study Intervention after the End of the Study

Participants will not receive any additional treatment with either GSK3965193 or bepirovirsen after completion of the study.

## 6.7. Treatment of Overdose

For this study, any dose of GSK3965193 CCI or bepirovirsen greater than CCI within a 24-hour time period will be considered an overdose.

GSK does not recommend specific treatment for an overdose. The investigator will use clinical judgement to treat an overdose.

In the event of an overdose, the investigator or treating physician should:

1. Contact the Medical Monitor immediately.
2. Closely monitor the participant for AE/SAE and laboratory abnormalities for at least 4 days.
3. Obtain a plasma sample for PK analysis immediately unless a PK sample has already been obtained after the overdose.
4. Document the quantity of the excess dose as well as the duration of the overdosing in the CRF.

Decisions regarding dose interruptions or modifications will be made by the investigator based on the clinical evaluation of the participant.

## 6.8. Concomitant Therapy

Any medication or vaccine (including over-the-counter or prescription medicines, recreational drugs, vitamins, and/or herbal supplements) or other specific categories of interest that the participant is receiving at the time of enrolment or receives during the study must be recorded along with:

- reason for use
- dates of administration including start and end dates
- dosage information including dose and frequency

CCI

In Parts 3 and 4 nucleos(t)ide analogs taken by participants for CHB treatment and oral contraceptives as detailed in Section 10.4 are permitted. Participants must abstain from taking prescription or non-prescription drugs (including vitamins, recreational drugs, and dietary or herbal supplements) within 7 days (or 14 days if the drug is a potential enzyme inducer) or 5 half-lives (whichever is longer) before the start of GSK3965193 until 14 days after the last dose, unless, in the opinion of the investigator, the medication will not interfere with the study. CCI

CCI  
[REDACTED]

Traditional Chinese medicine and/or acupuncture as it relates to CHB therapy should be avoided during the duration of the study. If participants report use of traditional Chinese medicine and/or acupuncture, then details must be recorded in the concomitant medication CRF.

#### **6.8.1. Nucleos(t)ide Treatment during and after the End of the Study (Parts 3 and 4)**

The investigator is responsible for ensuring that consideration has been given to the care of the participant's medical condition, and that participants are able to continue their NA therapy over the duration of the study.

The investigator is responsible for ensuring that consideration has been given to the post-study care of the participant's medical condition, whether or not GSK is providing specific post-study treatment.

#### **6.8.2. Prohibited Medications and Non-Drug Therapies**

The following concomitant medications are not permitted during the study.

- PEG-interferon or other immunomodulating therapies
- Immunosuppressing drug (e.g., prednisone) use >2 weeks duration from 3 months prior to randomization through to the final Follow-up visit (see Section 5.2)
- Prior treatment with any oligonucleotide or siRNA within 12 months prior to the first dosing
- Creatine-containing gym supplements
- Hepatitis B virus vaccinations
- Regular use of anti-coagulation therapies (e.g., warfarin, Factor Xa inhibitors or anti platelet agents like clopidogrel) or regular use of aspirin during bepirovirsen treatment

## 7. DISCONTINUATION OF STUDY INTERVENTION AND PARTICIPANT DISCONTINUATION/WITHDRAWAL

### 7.1. Discontinuation of Study Treatment

In rare instances, it may be necessary for a participant to permanently discontinue study treatment. A participant may discontinue study treatment at any time at his/her own request. Additionally, study treatment may be withdrawn at any time at the discretion of the Investigator for safety, behavioural or administrative reasons.

If study treatment is permanently discontinued, the participant will remain in the study to be evaluated for safety and efficacy assessments. If a participant discontinues study treatment, an early discontinuation (ED) visit should be performed. See the SoA for data to be collected at the time of discontinuation of study treatment.

Following the ED visit the participant will enter the follow-up/post-treatment period following the visit schedule and required assessments that need to be completed, per the SoA.

In Part 3 of the study participants who discontinue study treatment during the GSK3965193 (or placebo) monotherapy phase should complete an ED visit and enter the two-week CCI follow-up/washout period. If the participant CCI and consented to optional bepirovirsen, progression into the optional bepirovirsen treatment period must not occur unless this has been discussed and agreed with the Medical Monitor prior to the day 43 visit.

If the patient withdraws consent to participate in the study completely the procedure described in Section 7.2 should be followed.

Stopping criteria, including their evaluation and confirmation, are detailed in Section 7.1.1 to Section 7.1.7. Participants meeting these criteria should be monitored until laboratory abnormalities resolve, stabilize, or return to within baseline values as indicated. This may be done at follow-up visits specified in the SoA or require additional visits to be scheduled.

Study treatment may be discontinued, and the participant potentially withdrawn from the study, if:

- A participant experiences a serious or severe clinically significant AE that in the clinical judgement of the Investigator, is possibly, probably or definitely related to investigational product.
- The participant initiates treatment with any prohibited medications.
- Individual or study level stopping criteria are met
- Deviation(s) from the protocol
- Withdrawal of consent by participant (or proxy)
- Discretion of the Investigator

- Participant is lost to follow-up
- Closure or termination of the study

In the event of any of the following, ongoing dosing will be halted for all participants in a dose group/cohort:

- Two or more participants in the same dose group/cohort experience non-serious severe AEs considered at least possibly related to the administration of GSK3965193. These two AEs do not need to be within the same system, organ, or class.
- Any participant experiences an SAE considered at least possibly related to the administration of GSK3965193. The dosing will be temporarily halted, and no further participants will be dosed until a full safety review of the study has taken place. Relevant reporting and discussion with the GSK medical monitor, relevant GSK personnel, and with the CA and Institutional Review Board (IRB)/Independent Ethics Committees (IEC) will then take place prior to any resumption of dosing, which may also include the evaluation of lower doses. If following an internal safety review, it is appropriate to restart the trial, a substantial amendment will be submitted to the Regulatory Agencies and ethic committees. The trial will not restart until the amendment has been approved by the Agency(s) and ethic committee(s).

#### **7.1.1. Liver Chemistry Monitoring and Stopping Criteria**

**Liver chemistry stopping, and increased monitoring criteria** have been designed to assure participant safety and evaluate liver event etiology.

Discontinuation of study intervention for abnormal liver tests is required when:

- a participant meets one of the conditions outlined in the algorithm or
- in the presence of abnormal liver chemistry not meeting protocol-specified stopping rules, if the investigator believes that it is in the best interest of the participant.

#### **Part 3 (GSK3965193 Monotherapy)**

Study intervention will be discontinued for a participant if liver chemistry stopping criteria in [Figure 3](#) are met.

CCI

Refer to Section 10.6 for required liver safety actions, monitoring and follow-up to assess causality of liver event. Participants who do not meet protocol-specified liver event stopping criteria but met protocol-defined increased monitoring criteria may continue study intervention with liver chemistry monitoring at least weekly. Monitoring may take place at visits scheduled in the SoA, or additional visits as needed.

### **Part 3 (Bepirovirsen Monotherapy) and Part 4**

Liver chemistry stopping, and increased monitoring criteria have been designed to assure participant safety and evaluate liver event etiology.

Discontinuation of study intervention for abnormal liver tests is required by the investigator when a participant meets one of the conditions outlined in Table 8 or in the presence of abnormal liver chemistries not meeting protocol-specified stopping rules if the investigator believes that it is in best interest of the participant.

Table 8 lists the criteria for withholding or discontinuing the study medication in a study participant with elevation of ALT. Additional testing will be performed (see safety follow-up procedures for participants who meet increased monitoring or stopping criteria) and the participant monitored until liver chemistry abnormalities resolve, stabilize, or return to within baseline values.

If any of the criteria in [Table 8](#) are met every attempt must be made to have the participant evaluated (as soon as possible; preferably within 24 hours) for repeat assessment of liver chemistries and additional testing and close monitoring (a specialist or hepatology consultation is recommended). Participants must be monitored twice weekly until liver chemistry abnormalities (ALT, AST, alkaline phosphatase, bilirubin) resolve, stabilize, or return to within baseline values. Monitoring blood tests can be performed at scheduled visits in the SoA though additional unscheduled visits may be required depending upon the frequency of monitoring required. If study treatment is discontinued then an early discontinuation visit should be conducted and the participant will enter into the follow-up visit schedule as described in [Section 7.1](#).

**Table 8      Part 3 (Bepirovirsen Monotherapy) and Part 4 liver chemistry monitoring and stopping criteria**

CCI

**Notes:**

- Any abnormal laboratory parameters that meet the criteria for individual treatment discontinuation must be confirmed by retest of a new collection of blood samples as soon as possible.
- Deterioration considered clinically significant from the baseline liver parameters must be confirmed by retesting ALT, total bilirubin, direct bilirubin, and INR (if available).
- As a reminder for investigators/sites, if local laboratory assessments are used for decision-making, collect central labs in parallel and record local results in the CRF.
- If one criterion in the list above is met and confirmed by retesting, further treatment may be discontinued for this participant. Results of retesting must be evaluated before the next dose is administered.
- Monitor participant until liver chemistry abnormalities resolve, stabilize, or return to within baseline values.
- Cases such as Gilbert syndrome, where baseline bilirubin values are high, should be discussed with the Medical Monitor, to assess if it is a case of DILI or the participant may continue with dosing.

The procedures listed below are to be followed if a participant meets any of the liver event criteria defined in [Table 8](#).

- Notify the Medical Monitor within 24 hours of learning of the abnormality to confirm the participant's study treatment cessation and follow-up.
- Complete the Liver Event CRF.
- Complete the "Safety Follow-up Procedures" listed below.

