**Part 3 (Bepirovirsen Monotherapy) and Part 4**

Phase 2 liver chemistry stopping and increased monitoring criteria have been designed to assure participant safety and evaluate liver event etiology.

The procedures listed below are to be followed if a participant meets any of the liver chemistry stopping criteria defined in Section 7.1.1.

- Immediately withdraw the participant from study treatment.
- Notify the Medical Monitor within 24 hours of learning of the abnormality to confirm the participant's study treatment cessation and follow-up.
- Complete the Liver Event CRF.
- Complete the "Safety Follow-up Procedures" listed below

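### For Part 3 bepirovirsen and Part 4, the note to Table 8 makes stopping after a confirmed liver criterion optional, while Section 7.1.1 and Appendix 6 make it mandatory

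*Protocol*

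**What the plan says.** Four statements in the current protocol bear on what a site does when a liver criterion is met.

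- **Section 7.1.1, opening text.** Discontinuation is required when a participant meets a condition in the algorithm. It is also required when values fall short of the rules but the investigator thinks stopping is in the participant's interest.
- **Section 7.1.1, Part 3 (Bepirovirsen Monotherapy) and Part 4.** Discontinuation "for abnormal liver tests is required by the investigator when a participant meets one of the conditions outlined in Table 8". The same subsection describes the table more broadly: "Table 8 lists the criteria for withholding or discontinuing the study medication in a study participant with elevation of ALT".
- **Section 7.1.1, Notes to Table 8.** "If one criterion in the list above is met and confirmed by retesting, further treatment may be discontinued for this participant". The first note in the set reads: "Any abnormal laboratory parameters that meet the criteria for individual treatment discontinuation must be confirmed by retest of a new collection of blood samples".
- **Section 10.6 (Appendix 6), Part 3 (Bepirovirsen Monotherapy) and Part 4.** "The procedures listed below are to be followed if a participant meets any of the liver chemistry stopping criteria defined in Section 7.1.1". The first procedure listed is to withdraw the participant from study treatment immediately.

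The notes also contain two safeguards and one exception. The safeguards are "Results of retesting must be evaluated before the next dose is administered" and "Notify the Medical Monitor within 24 hours of learning of the abnormality to confirm the participant's study treatment cessation and follow-up". The exception is for cases such as Gilbert syndrome with a high baseline bilirubin, which "should be discussed with the Medical Monitor, to assess if it is a case of DILI or the participant may continue with dosing". The visible sentence of Section 7.1.9 says that treatment may not be restarted once any stopping criterion has been met.

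**The concern.** A stopping rule should give one instruction. Here the verb is permissive in the note and mandatory in the body text and in Appendix 6, for the same study parts. A site working from the note alone could regard the next bepirovirsen injection after a confirmed stopping value as a matter of judgement.

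Sites are also sent to different texts. The risk table in Section 2.3.1 points to Section 7.1.1 for liver monitoring, hold and stopping criteria. The section on ALT increases as an event of special interest (8.3.7.2.1) points to Section 10.6. The first route includes the permissive note; the second leads to immediate withdrawal. Section 2.3.1 expects ALT flares from bepirovirsen in both parts, so the rule is likely to be consulted.

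At stake are the safety of individual participants and consistency between sites. No effect on the Part 4 response rate or on the comparison of arms is claimed.

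**Working it through.** No arithmetic applies, and there is no figure in the plan to reproduce. The check is to set the statements side by side and ask whether they can all be followed.

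1. **Same study parts?** Yes. The 7.1.1 subsection, its notes and the Appendix 6 subsection all concern Part 3 bepirovirsen and Part 4. The opening of 7.1.1 is general. It refers to an algorithm and does not name Table 8, so it supports the mandatory reading without being essential to it. All are current text, not amendment history.
2. **Same criteria?** Yes, for discontinuation. The note refers back to the list above it, which is Table 8. The body text names Table 8. Appendix 6 takes its stopping criteria from Section 7.1.1, where Table 8 sits.
3. **Does the permissive note concern only holds?** No. The first note requires a retest for values meeting the criteria for individual treatment discontinuation. The later note speaks of a criterion met and confirmed by retesting, so it reaches at least those values.
4. **Is general discretion granted elsewhere?** Not in the liver text. Section 7.1.1 gives the investigator judgement in one direction only, to stop for values that do not meet the rules. The one visible route to continued dosing is the Gilbert-type case, discussed with the Medical Monitor. That exception would hardly be needed if the note already gave general discretion.
5. **Does Section 7.1 settle it?** No. Its general list of reasons for stopping is also worded permissively, but the same section refers the evaluation and confirmation of stopping criteria to 7.1.1 through 7.1.7.
6. **Which wording is out of line?** The note. Of the four liver-specific statements, three order stopping and one permits it. The notification step beneath the note presupposes that treatment has ceased, and 7.1.9 bars restart.
7. **Is the mandatory sentence itself well drawn?** Not quite. It attaches the requirement to every Table 8 condition, yet the table is said to hold withholding criteria too. Taken literally, a hold-level value would require discontinuation.

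The thresholds in Table 8 are redacted, so the number of participants who would reach a stopping criterion cannot be calculated.

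**The case against.** The strongest reply is that Table 8 cannot be seen. Its title covers monitoring as well as stopping, and the surrounding text speaks of withholding. In a graded table each row may carry its own action, and the note's verb may be a general one that gives way to the row. The body text itself uses a conditional when it describes what follows if treatment is discontinued. A site would also have to overlook a mandatory sentence in the same subsection and a notification step just below the note.

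Much of this stands. A row that orders stopping cannot be excluded, and it would reduce the risk further. It would not make the note agree with the body text for discontinuation rows, because the conflicting sentences are themselves unredacted.

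Two stronger readings are tempting but unsupported.

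- A reader might infer that the two procedure lists contradict each other, because the list after Table 8 has no withdrawal step and the one in Appendix 6 does. Their triggers differ. The first applies to any liver event criterion in Table 8, and its follow-up heading covers monitoring and stopping criteria. The second applies to stopping criteria only. A wider trigger without withdrawal and a narrower one with it is coherent. Making the lists identical would either impose withdrawal on hold-level values or remove it from Appendix 6.
- A reader might infer that Appendix 6 dispenses with the retest. It draws its criteria from 7.1.1, whose notes require confirmation, so *immediately* can be read as following a confirmed result. What is missing is a pointer.

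**Conclusion.** The inconsistency is real and confined to wording. For confirmed discontinuation-level values the note permits what the body of 7.1.1 and Appendix 6 require, and the body text applies its requirement too widely. The mandatory reading is clearly the better supported, so the note should change.

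The practical size is small. The retest has to be evaluated before another dose, the Medical Monitor hears within 24 hours, the body text asks for liver monitoring twice weekly, and restart is barred. A reader might go further and count the weekly injections still to come after a stopping value as the exposure at risk. The documents do not support that count: they give neither the timing nor the frequency of such values, and the safeguards stand between the note and any further dose.

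The conclusion assumes that Table 8 contains discontinuation criteria, as the visible text says, and that the redacted remainder of 7.1.9 does not reverse its first sentence. It assumes nothing about thresholds or row-level actions. Severity: a minor safety-wording correction.

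**What to change.** Make three wording changes in the protocol.

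1. **Notes to Table 8.** Replace *may* with *must* for Table 8 discontinuation criteria that are met and confirmed by retest. Keep the Gilbert-type exception, discussed with the Medical Monitor.
2. **Section 7.1.1 body text, Part 3 bepirovirsen and Part 4.** Limit the requirement to the discontinuation criteria, and leave each hold criterion to its own stated action.
3. **Appendix 6, same parts.** Add a short cross-reference saying that dosing is held pending the retest described in 7.1.1 and that withdrawal is immediate once the value is confirmed.

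Leave the two procedure lists as they are. The cost is a text amendment in three places and a memo to sites, with no new assessments.

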**Safety Follow-up Procedures for Participants Who Meet Any of The Liver Monitoring and Stopping Criteria:**

Viral hepatitis serology including:

- Hepatitis A IgM antibody
- Cytomegalovirus IgM antibody
- Epstein-Barr viral capsid antigen IgM antibody (or if unavailable, obtain heterophile antibody or monospot testing)
- Hepatitis E IgM antibody.
- Hepatitis B virus DNA load
- Hepatitis C virus RNA load
- Hepatitis D virus antibody

Obtain a blood sample for PK analysis as soon as possible following the occurrence of an event. Record the date/time of the PK blood sample collection and the date/time of the last dose of study treatment prior to blood sample collection on the CRF. If the date or time of the last dose is unclear, provide the participant's best approximation. Instructions for sample handling and shipping are included in the Laboratory Manual.

Review INR.

Serum creatine phosphokinase (CPK) and lactate dehydrogenase (LDH).

Review fractionated bilirubin, if total bilirubin  $\geq 1.5 \times \text{ULN}$

Assess eosinophilia.

Record the appearance or worsening of clinical symptoms of hepatitis (fatigue, nausea, vomiting, right upper quadrant pain or tenderness, fever, rash or eosinophilia) as relevant on the AE CRF.

Record use of concomitant medications, acetaminophen, herbal remedies, other over the counter medications, or putative hepatotoxins on the Concomitant Medications CRF.

Record alcohol use on the Liver Events CRF.

The following are **required for participants who meet the ALT and bilirubin stopping criteria** but are optional for other abnormal liver chemistries.

- Anti-nuclear antibody, anti-smooth muscle antibody, Type 1 anti-liver kidney microsomal antibodies and quantitative total immunoglobulin G (IgG or gamma globulins).
- Serum acetaminophen adduct high performance liquid chromatography (HPLC) assay (quantifies potential acetaminophen contribution to liver injury in participants with definite or likely acetaminophen use in the preceding week [James, 2009]).
- Liver imaging (ultrasound, magnetic resonance, or computerized tomography) or Liver biopsy to evaluate liver disease.
- The Liver Imaging and/or Liver Biopsy CRFs are also to be completed if these tests are performed.

